## **Study Protocol:**

**Title:** Single Session of Fecal Microbiota Transplantation in Decompensated Cirrhosis: An open-label randomized control trial

## **INTRODUCTION**

Cirrhosis of liver is the culmination point of long-standing chronic liver disease hallmark by the cardinal features of liver fibrosis and portal hypertension. The prognosis of patients with cirrhosis is punctuated by the onset of complications which denote the stage of decompensation characterized by ascites, hepatic encephalopathy (HE) and variceal bleeding. Onset of decompensation heralds concomitant complications like renal dysfunction, immune dysregulation, pulmonary and cardiac dysfunction as well as bacterial infections including spontaneous bacterial peritonitis accounting for significant morbidity and mortality.

The role of human gut microbiota in health and disease has received considerable attention. The gut microbiome consists of over 1014 microorganisms, including bacteria, fungi, viruses and archaea, which co-exist in a symbiotic relationship. A majority comprises anaerobic bacteria. A healthy gut microbiome enhances metabolism, resilience to infection and inflammation, and resistance to cancer and autoimmunity. The microbiome may mediate these effects by secretion of factors that modulate intestinal permeability, the mucus layer, epithelial cell function, innate and adaptive immunity and intestinal motility. A disruption of this microbial symbiosis is intestinal dysbiosis, which adversely affects these functions and is implicated in the pathogenesis of disease. The gut is connected to the liver by the portal tract, and hence qualitative and quantitative changes in the gut microbiome play a pivotal role in the pathogenesis of alcoholic liver disease, as well as other liver diseases.

Patients with cirrhosis have been demonstrated to have significant changes in their gut microbiota characterized by alteration in the intestinal microbiome (gut dysbiosis) as well as small intestinal bacterial overgrowth (SIBO). In a study with patients with cirrhosis from China it has been reported that the proportion of phylum *Bacteroidetes* was decreased, and those of *Proteobacteria* and *Fusobacteriawere* highly enriched in the faeces of these patients. On the other hand a study from the United States has shown higher prevalence *Alcaligenaceae*,

Enterobacteriaceae, and Fusobacteriaceae while those belonging to Ruminococcaceae and Lachnospiraceae were found in a lower proportion. In this perspective a proposed index called cirrhosis dysbiosis ratio (CDR) of the amounts of beneficial autochthonous taxa (Lachnospiraceae + Ruminococcaceae + Veillonellaceae + ClostridialesIncertaeSedis XIV) and potentially pathogenic taxa (Enterobacteriaceae + Bacteroidaceae) has been found to core-relate inversely with model of end-stage liver disease (MELD) score and 30 day mortality thus suggesting an integral role of gut dysbiosis in the prognostic outcome of cirrhosis.

Gut dysbiosis has been closely linked to the complications associated with decompensated cirrhosis. Several studies have documented the alteration of gutmicrobiota in patients with hepatic encephalopathy. Liu et al found an overgrowth of potentially pathogenic Escherichia coli (E. coli) and Staphylococcus spp. in the feces of patients with liver cirrhosis (70%–80% related to HBV or HCV) and MHE. Another study showed that patients with cirrhosis and HE had a higher abundance of fecal Enterobacteriaceae, and Alcaligenaceae compared with control subjects.

Therapeutic modalities that restore normal gut flora and stabilize the gut liver axis are being extensively studied in the management of cirrhosis and its complications. Antibiotics, probiotics and long chain fatty acid supplementation are being evaluated as methods to restore gut eubiosis and consequently limit progressive liver damage.

Fecal Microbiota Transplantation (FMT) involves the infusion of intestinal microorganisms by the transfer of stool from a healthy individual into a diseased individual for restoration of normal intestinal flora.Methods to infuse stool include a nasogastric tube or gastroscopy, or into the colon through a colonoscope or rectal catheter. The ultimate goal of FMT is to replace aberrant native microbiota with a stable community of donor microorganisms. The treatment is based on the premise that an imbalance in the community of microorganisms residing in the gastrointestinal tract (i.e., dysbiosis) is associated with specific disease states. FMT has been well-established as a treatment modality to stably modify the gut microbiome and has been shown to be safe and efficacious in several disease states resulting from gut dysbiosis including Clostridiumdifficile infection and inflammatory bowel disease.

With this background it is hypothesized that in patients with advanced cirrhosis FMT may reduce the progression to chronic liver failure including jaundice, accumulation of fluid

within the abdominal cavity, bleeding, encephalopathy and the development of infection and organ dysfunction. A trial is proposed to determine whether a FMT from a healthy donor to a patient with advanced cirrhosis is both feasible and safe and to assess its impact on overall survival and prognosis.

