**Aim:**

To determine the role of FMT in improving liver function, prognostic scores, and short term mortality and reducing complications in patients with DC

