**Objectives:**

**Primary Objective:** To assess the difference in 180-day mortality between the FMT group and the SOC group.

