**Secondary Objective**

1. To assess and compare the changes in liver function in both groups based upon
  - CTP score at 28 days, 90 days and 180 days
  - MELD Score at 28 days, 90 days and 180 days
  - MELD Na Score at 28 days, 90 days and 180 days
2. To compare the complications in both groups in a follow-up period of 180 days
3. Changes in inflammatory markers (IL-1b, IL-6) in both groups at 28 days

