#### **4. METHODOLOGY**

**Study design:** This will be an institute based prospective pilot study carried out in Postgraduate Institute of Medical Education and Research, Chandigarh from July 2018 to June 2020.

**Study period:** 15 months (from August 2018 to November 2019)

**Recruitment Period:** 10 months (August 2018 to May 2019)

**Sample Size:** 20 consecutive patients satisfying the selection criteria in each arm

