### **Pre FMT**

Participants randomized to the FMT arm will be given pretreatment antibiotics to decrease the host bacterial load, lower diversity, and enable a colonic colonization of the donor microbiota. Lactulose and rifaximin will be continued for all patients as per indication. A 5-day broad-spectrum coverage regimen will be used (metronidazole 500 mg orally three times daily, ciprofloxacin 500 mg orally twice-daily, and amoxicillin 500 mg orally three times daily) prior to administration of FMT. All antibiotics will be discontinued at least 12 hours before FMT to ensure that these agents would not impact the instilled microbiota. Participants in the SOC arm will not receive antibiotic pretreatment or FMT, but follow-up will be identical on days 7, 30 and 90 post FMT post randomization.

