### **Follow Up post FMT**

Follow up of patients will be done at 7, 30, 90 and 180 days post FMT. During follow up patients will be evaluated for clinical parameters, routine biochemical monitoring and inflammatory markers for determining status of disease status.

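### Feasibility and safety are a stated purpose, but feasibility has no measure, safety has only mortality and an undefined complications comparison, and an unclear time origin may leave the FMT arm's pretreatment period uncounted

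*Combined protocol and SAP*

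**What the plan says.** The last paragraph of the Introduction proposes a trial to find out whether FMT from a healthy donor in advanced cirrhosis "is both feasible and safe and to assess its impact on overall survival and prognosis". The Methodology section gives the design as follows: "This will be an institute based prospective pilot study". It plans 20 patients per arm.

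The formal aims are narrower. The Aim covers liver function, prognostic scores, "short term mortality and reducing complications in patients with DC". The primary objective is "To assess the difference in 180-day mortality between the FMT group and the SOC group". The secondary objectives are CTP, MELD and MELD-Na scores, then "To compare the complications in both groups in a follow-up period of 180 days", then "Changes in inflammatory markers (IL-1b, IL-6) in both groups at 28 days". None of them names feasibility, safety or adverse events.

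On timing, the section Follow Up post FMT states: "Follow up of patients will be done at 7, 30, 90 and 180 days post FMT". Visit content there is clinical parameters, routine biochemistry and inflammatory markers. The Pre FMT section states: "Participants randomized to the FMT arm will be given pretreatment antibiotics to decrease the host bacterial load". This is a five-day course of three oral drugs, stopped no less than 12 hours ahead of the instillation. The SOC arm receives neither the antibiotics nor FMT. The same section says SOC follow-up will match on days 7, 30 and 90, and names both FMT and randomisation as the starting point in one phrase.

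The Statistical Analysis section lists generic tests, time points up to day 90 and in-hospital survival curves. It contains no adverse-event or feasibility analysis.

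**The concern.** A pilot trial of a new procedure is usually relied on for two things: whether the procedure can be delivered, and what harm it does. Here both are announced as a purpose and neither is carried into the objectives or the analysis.

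Feasibility is a real question in this design. Donors must be family members, because no pooled facility exists, and the donor exclusions are long (even occasional alcohol use excludes). Neither the eligibility criteria nor the randomisation section requires a suitable donor to have been found. A patient can therefore be randomised to FMT and never receive it. The plan does not count such patients, and visits timed from FMT give them no follow-up dates.

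For safety, no outcome is named that would capture harms of the tube, the instillation or the antibiotics. The arms also lack a common clock. SOC patients have no FMT date, and FMT patients have a treated period between randomisation and FMT. If time is counted from FMT in one arm and from randomisation in the other, the comparison loses a window in one arm only, and that window contains part of the experimental strategy.

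**Working it through.** **1. Purpose set against measures**

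| Stated purpose | Objective | Data collection named | Analysis named |
|---|---|---|---|
| Feasibility | none | none | none |
| Safety | none by name; mortality and complications bear on it | no adverse-event collection | generic chi-square or Fisher's exact test could be applied to complications |
| Survival | 180-day mortality | visits to day 180 (Follow Up post FMT) | in-hospital Kaplan-Meier curves; time points stop at day 90 |

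The Research question, Study Hypothesis and Aim treat complications as events that FMT should prevent or reduce. The secondary objective does not define the term.

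**2. Time origins set side by side**

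- Follow Up post FMT: days 7, 30, 90 and 180, from FMT.
- Assessment of Pro-inflammatory Cytokines: day 28, from FMT.
- Pre FMT: days 7, 30 and 90, with both FMT and randomisation named; day 180 absent.
- Primary objective and complications objective: 180 days, no origin given.
- Statistical Analysis: no origin given.

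**3. Length of the window that may go uncounted**

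Inputs from the Pre FMT section: 5 days of antibiotics and at least 0.5 day of washout, both after randomisation and in the FMT arm only.

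- Minimum window: 5 + 0.5 = 5.5 days per patient.
- Share of 180 days: 5.5 / 180 = 3.1%.
- Across 20 patients: 20 × 5.5 = 110 patient-days.

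**4. Deaths expected in that window**

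The documents give no mortality rate, so 180-day mortality m is an assumption, with constant hazard. The risk in 5.5 days is p = 1 − (1 − m)^(5.5/180). Expected deaths are 20p, and the chance of at least one is 1 − (1 − p)^20.

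| Assumed m | p | Expected deaths in 20 | Chance of at least one |
|---|---|---|---|
| 10% | 0.0032 | 0.06 | 6% |
| 20% | 0.0068 | 0.14 | 13% |
| 30% | 0.0108 | 0.22 | 20% |
| 40% | 0.0155 | 0.31 | 27% |

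**5. What 20 FMT patients could show once these outcomes are measured**

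The plan gives no rationale for 20 per arm, so there is no sample-size figure of its own to reproduce.

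- Zero events in 20: two-sided 95% upper limit 1 − 0.025^(1/20) = 16.8%; one-sided 1 − 0.05^(1/20) = 13.9%.
- Chance of at least one event: 1 − 0.95^20 = 64% if the true rate is 5%; 1 − 0.90^20 = 88% if it is 10%.
- Feasibility, exact 95% CI: 18/20 gives 68.3% to 98.8%; 20/20 gives 83.2% to 100%.

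These figures in step 5 hold for any 20 patients. They show what the repaired trial could conclude and do not measure the size of the gap.

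**The case against.** A reader might infer that the plan measures nothing about safety. The documents do not support that. Mortality and complications are compared between arms, and the Introduction counts infection, bleeding, encephalopathy and organ dysfunction among the consequences of advanced disease. Serious harm from FMT could appear in those events, and a between-arm comparison shows excess as well as reduction. Because the complications objective is undefined, it also cannot be said to exclude procedural harms. What stands is that the safety information is indirect and undefined, and that no adverse-event collection is named. For feasibility the absence is complete in the text reviewed.

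A reader might also infer that the plan leaves out the pretreatment period, so that FMT-arm harms will be under-counted. That too goes further than the text. The FMT-based visit schedule implies it, but the Pre FMT section also names randomisation, the 180-day objectives give no origin, and an event during pretreatment could still be recorded at the day-7 visit. Nor does the plan show that pretreatment is when the arms differ most, since the instillation itself comes later. What stands is an ambiguity that may lead to uncounted events.

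Two further points are fair. The feasibility and safety purpose rests on one sentence in the Introduction, and deleting it would remove that inconsistency. It would leave the time origin unresolved and a pilot without a feasibility result. Also, the text reviewed ends at Annexure 1, so an adverse-event form placed after it cannot be ruled out. The objectives, follow-up and statistics sections are present, and they show the gap.

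**Conclusion.** The concern holds in a limited form. Followed as written, the plan cannot answer its feasibility question and can answer its safety question only through mortality and an undefined complications comparison.

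The time origin is unclear, and at least 5.5 days of FMT-arm time per patient may fall outside the count. On assumed 180-day mortality of 10% to 40% and a constant hazard, this involves 0.06 to 0.31 expected deaths, so the primary comparison is unlikely to turn on it. The greater losses would be antibiotic-related harms and patients randomised to FMT who never reach it. Their number cannot be estimated from the documents.

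The change should be made, because it is cheap and lets the pilot report on its stated purpose.

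**What to change.** 1. **Time origin.** In Pre FMT, Follow Up post FMT and Statistical Analysis, make randomisation time zero in both arms for mortality, complications, adverse events and visits. Include day 180 in both arms, and follow every randomised patient whether or not FMT is given.
2. **Safety.** Add to the secondary objectives and the statistical section a between-arm comparison of patients with any serious adverse event, and of patients with any new infection, from randomisation to day 180. Report each as a risk difference with an exact 95% CI. Add a descriptive listing of non-serious events related to the antibiotics, tube or instillation. Define complications so that the overlap with these outcomes is clear.
3. **Feasibility.** Report, with an exact 95% CI, the proportion of patients randomised to FMT who have an eligible donor, complete pretreatment and receive the full instillation.
4. **Interpretation.** State in advance that 0/20 leaves a two-sided 95% upper limit of 16.8%, so that absence of an event is not read as evidence of safety.

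Cost: one more form at existing contacts, one summary table, and a small shift in FMT-arm visit dates. The Pre FMT section omits day 180 for SOC, but the primary objective already needs that assessment. No treatment or procedure changes.

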## **2. REVIEW OF LITERATURE**

Microbiota refers to the bacteria, archaea, microeukaryotes, fungi and viruses that share the human body space, so as to function in a commensal, symbiotic, or pathogenic relationship with the host. The human microbiota is estimated to contain 10-100 trillion microbial cells.

Microbiome refers to the collective genomes of all the above-mentioned microorganisms. The microbiome is commonly used interchangeably with microbiota – even though this usage is incorrect. The gut microbiota is composed of 100 trillion bacteria of diverse taxonomy . The microbiome has 150-fold more genes than the human genome of which over 99% of the genes are bacterial which is why we study that what is predominant.

Disruption of the healthy microbiota in both composition and functionality is dysbiosis – in which pathogenic species predominate leading to various disease conditions. The term pathogenic species in this context could be better utilized to an increase in numbers and functionality of those that promote/participate in deleterious functional metabolic outcomes that affect the host adversely rather than just the numbers of pathogenic species per say – for example pathogenic species such as E.coli and K.pneumonia are all normal components of the gut microbiota in healthy state (probably in lesser numbers) – however, in the presence of a modifying factor, say for example alcohol or high fat diet – their number and functions are adversely modified to promote adverse metabolism/metabolic product accumulation in the host.

Multiple studies have shown association of gut dysbiosis with cirrhosis and its complications. In a study from Wang et al FMT exerted protective effects in hepatic encephalopathy (HE) in rats, and improved the cognitive function with improvement of overall

the liver function indexes. FMT may cure HE by altering the intestinal permeability and improving the TLR response of the liver. This study was the index study to establish a rat model of hepatic encephalopathy and then prospectively carried on the FMT. The results unequivocally hinted that FMT can serve as a kind of new method for the treatment of hepatic encephalopathy.

The first human report of utility of FMT in HE was shown by Kao et al where dramatic clinical improvements, both subjectively and objectively, following serial FMT were observed. This case study demonstrated that serial FMT can result in cognitive improvement in mild HE.

Bajaj et al demonstrated the first trial that showed that FMT from a rationally selected donor reduced hospitalizations, improved cognition, and dysbiosis in cirrhosis with recurrent HE. In this study a specified beneficial population of bacterial community from a stool bank was used.

The following table summarizes the some of the other major studies demonstrating the utility of FMT in cirrhosis

Authors	Methodology	Hallmarks of the study
Chen et al.2011	Controls vs. patients with alcoholic and hepatitis B cirrhosis	First major study of stool microbiome in cirrhosis. Showed that fecal microbiome in cirrhosis is distinct, including increase in bacteroidetes (Bacteroidaceae) and proteobacteria and reductions in autochthonous taxa, such as Lachnospiraceae. Streptococcaceae and positively correlated with cirrhosis severity.
Bajaj et al. 2012	Controls vs. all etiology OHE and no OHE cirrhosis.	First study of stool microbiome in cirrhotics with and without Overt Hepatic Encephalopathy (OHE) that looked at correlation-network analysis between microbiome, endotoxemia and cognition. HE was associated with reduced abundance of Lachnospiraceae and ruminococcaceae and increased

		Enterobacteriaceae. Increased inflammation and endotoxemia were noted in HE groups..
Mutlu et al. 2012	Healthy controls vs. alcohol cirrhosis	Study of sigmoidal mucosa microbiome that showed lower median abundance of Bacteroidetes and increased median abundance of proteobacteria in alcoholic cirrhotics
Bajaj et al. 2012	Controls vs. all etiology OHE and no-OHE cirrhosis.	First major study to compare changes in sigmoid mucosal microbiome in all etiology with stool microbiota in cirrhotics with and without OHE. Mucosal microbiota analysis revealed increased enterococcus and Veillonella abundance in OHE. Roseburia was reduced in OHE and, along with other autochthonous microbes, showing positive co-relation with cognition and reduced inflammation in all groups. Enterococcus and Veillonella associated with poor cognition and inflammation.
Bajaj et al. 2014	Cirrhotics followed as outpatient(compensated and decompensated) and during inpatient decompensation.	First major study of cirrhosis stool microbiome comparing cirrhosis in compensated and decompensated state. Increased porphyromonadaceae, Bacteroidaceae, and Enterobacteriaceae with reduced Veillonellaceae, Ruminococcaceae, and Clostridiales XIV (Firmicutes) noted in compensated cirrhosis. Decompensation resulted in increased Enterobacteriaceae, Enterococcaceae, and Staphylococcaceae and reduced Bacteroidaceae. MELD score correlated negatively with Firmicutes and positively with Enterobacteriaceae. Introduction of CDR concept.
Bajaj et al.	Controls vs. all etiology cirrhosis studied before	First major study looking at the influence of PPI use on stool microbiota in cirrhosis. Streptococcaceae abundance was

2014	and after administration of PPI.	relatively increased in controls and cirrhotics after 14 days of PPI. First study that hypothesized oral microbiota could migrate distally secondary to change in intestinal protective mechanisms
Kakiyama et al. 2014	Controls vs. all etiology cirrhosis. Subgroups examined before and after rifaximin therapy.	First major study of role of BAs in gut microbiome modulation in cirrhosis. Showed increased Bacteroidaceae and reduced Veillonellaceae, Lachnospiraceae, and Ruminococcaceae in advanced cirrhosis. CDCA positively correlated with Enterobacteriaceae, while DCA positively correlated with Ruminococcaceae. Post rifaximin, early cirrhotics had reduced Veillonellaceae
Qin et al. 2014	Controls vs. all etiology cirrhosis followed over time.	Major study that cataloged human microbiome genes in cirrhotic stool samples. Increased Veillonella, Streptococcus, Clostridium, and Prevotella, with reduced bacteroides in cirrhosis.
Bajaj et al. 2015	Controls vs. all etiology cirrhosis with and without DM	Major study that compared stool and sigmoid mucosa microbiota in cirrhotics with and without DM. The study showed no change to in decompensated diabetic cirrhotics. Increased Enterococcaceae-relative abundance, reduced Bacteroidaceae, and increased Lactobacillaceae and Enterococcaceae were noted in compensated diabetic cirrhotics at the end of the study period.
Chen et al. 2015	Controls vs. all etiology cirrhosis with ACLF	Study evaluated stool microbiome of cirrhotics with ACLF. ACLF was associated with increased relative abundance of Pasteurellaceae, Streptococcaceae, and Enterococcaceae with decreased Bacteroidaceae, Lachnospiraceae, and Ruminococcaceae. OHE was associated with reduced Lachnospiraceae. On networkcorrelation analysis, strong linkage

		of Lachnospiraceae and Ruminococcaceae
Bajaj et al. 2015	Controls vs. all etiology cirrhosis with and without OHE.	First major study that explored stool and salivary microbiota in detail in all etiology cirrhotics and further explored the changes with decompensation. Significantly increased Enterobacteriaceae and Enterococcaceae, with reduced Lachnospiraceae, Ruminococcaceae, and ClostridialesIncertaeSedis XIV noted in the saliva from compensated cirrhotics. Similar microbiota was noted to be prominent in cirrhotics with prior OHE. Streptococcaceae in the saliva was significantly higher in the stool for both groups.
Ahluwalia et al. 2016	Controls vs. all etiology cirrhosis with and without OHE.	Study looked at stool microbiota of cirrhotics with OHE. OHE patients had higher relative abundance of autochthonous bacteria with higher abundance of Enterococcaceae, Staphylococcaceae, Porphyromonadaceae, and Lactobacillaceae. MR spectroscopy showed autochthonous taxa correlated negatively and Enterobacteriaceae correlated positively with disease.

